# 10.5.1.3 Multiplicity Strategy and Testing Hierarchy

The efficacy analyses will employ a serial gatekeeper strategy to maintain the Type 1 error rate at  $\alpha$ =0.05 across the family of analyses that support the primary and key secondary objectives. The strategy specifies a hierarchy of significance tests where each test acts as a gatekeeper to the tests below it.

The primary and key secondary endpoints will be assessed in the following order beginning with comparisons of ZX008 0.8 mg/kg/day to placebo on

- The change in MCSF from baseline.
- The proportion of subjects who achieve a ≥40% reduction from baseline in convulsive seizure frequency.
- The proportion of subjects who achieve a ≥50% reduction from baseline in convulsive seizure frequency.
- The longest convulsive seizure-free interval.

The evaluation of key secondary endpoints continues by comparing the ZX008 0.2 mg/kg/day group to placebo in the following order:

- The change in MCSF from baseline.
- The proportion of subjects who achieve a ≥40% reduction from baseline in convulsive seizure frequency.
- The proportion of subjects who achieve a ≥50% reduction from baseline in convulsive seizure frequency.
- The longest convulsive seizure-free interval.

# 10.5.2 Safety Analyses

Summaries of safety data will be presented by treatment – ZX008 0.8 mg/kg/day, ZX008 0.2 mg/kg/day or placebo – separately for the Titration, Maintenance and T+M periods. The number and percentage of subjects in each treatment group with AEs will be displayed by body system and preferred term using the Medical Dictionary for Regulatory Activities (MedDRA). Summaries of AEs by severity and relationship to study drug will also be presented. A separate summary will be provided for all serious AEs (SAEs). Selected summaries will be repeated broken out by age group, ie, for ages <6 years and ≥6 years.

Hematology and chemistry laboratory results will be summarized using shift tables that tabulate the

Confidential Page 85 of 175

proportion of subjects who have lab results that change from baseline. Shift tables will be presented for each time point where lab results are collected. Mean change from baseline will also be calculated for continuous hematology and chemistry results at all time points available.

Laboratory tests, vital signs, physical examinations, neurological examinations, ECG, Doppler echocardiogram, C-SSRS, Tanner Staging results, etc, will be summarized appropriately, by treatment. All safety summaries will be based on the SAF Population.

# 10.5.3 Pharmacokinetic Analyses

All data will be evaluated using population PK analysis methods and the methods will be described in detail in a separate PK analysis plan. In brief, the plan is to use published data to construct a population PK model for fenfluramine in adults. Given the age range of subjects to be enrolled in this study, it will be possible to use the known ontogeny of drug disposition in children to predict fenfluramine PK in subjects with Dravet syndrome from the population PK model. The robustness of the empirical model will then be confirmed by applying the model to PK data collected from this study. In this way, the effect of body size, age, and any other relevant factors can be quantified to assure that an adequate understanding of fenfluramine PK is obtained.

The full methods and results of the population PK analysis of data from this study will be provided in a separate report. The clinical study report will contain a brief summary of the analysis including: the population mean and interindividual variability estimates from the fit of the population PK model; summary statistics of the plasma concentrations by PK sampling time and of the individual, derived plasma PK parameters (Cmax,  $AUC_{0-t}$ ,  $T_{max}$ , and  $t_{1/2}$ ) by treatment group. The clinical study report will also contain a comparison of the PK of fenfluramine in the children enrolled in this study to historical data from adults.

# 10.6 ANALYSES PROVIDED TO AN INDEPENDENT DATA AND SAFETY MONITORING COMMITTEE

A safety oversight monitoring plan will be in place with an IDSMC evaluating data from the subjects. Details will be provided in the IDMC charter. The IDSMC's primary responsibility is to ensure that study subjects are not exposed to unanticipated harm that could have been prevented by timely review and intervention. The IDMC is established to review safety data at predefined time points, and to recommend to the sponsor whether to continue, modify, or terminate the study as necessary. The IDMC is composed of expert permanent members who cover relevant specialties (neurology, cardiology, pediatrics, and statistics). The IDSMC members may request assistance from a number of additional and hoc members if needed.

# 11. ETHICAL & REGULATORY CONSIDERATIONS

#### 11.1 ETHICAL CONSIDERATIONS

The procedures set out in this study protocol are designed to ensure that the sponsor and the investigator abide by the principles of the current ICH GCP guideline on the conduct, evaluation and documentation of this study, as described in ICH Topic E6 Guideline. ICH GCP is an

Confidential Page 86 of 175

international ethical and scientific quality standard for designing, conducting, recording, and reporting studies that involve the participation of human subjects. Compliance with this standard provides public assurance that the rights, safety, and well-being of study subjects are protected, and that the clinical study data are credible.

The study will also be carried out according to all applicable international and national regulatory requirements.

The sponsor and the investigator must inform each other (eg, during a study initiation visit, via email, etc) that all ethical and legal requirements have been met before the first subject is enrolled into the study.

#### 11.2 INFORMED CONSENT

The investigator is responsible for obtaining a subject's written informed consent to participate in the study.

A Subject Information Sheet and a master ICF will be prepared by the sponsor according to the provisions of ICH GCP and local legal requirements.

All subjects will be informed that the study will be registered in the public database at ClinicalTrials.gov in accordance with the FDA Amendments Act of 2007 (Section 12.3).

Before undergoing screening procedures for possible enrollment into the study, subjects must be informed, in an understandable form, about the nature, scope, and possible consequences of the study. This information must be given orally to subjects by a physician or medically qualified person (according to applicable regulatory requirements) who is well informed about the nature, scope, and possible consequences of the study. Written information about the study will also be provided in a Subject Information Sheet. The date on which this oral and written information on the study was provided to the subject, and by whom it was provided, must be documented in the ICF.

As specified in ICH GCP Section 4.8 and the US 21CFR Section 50.25, the informed consent discussion must emphasize that participation in the study is voluntary and that subjects have the right to withdraw their consent at any time without giving a reason and without any disadvantage for their subsequent care.

Subjects must be given ample time and opportunity to inquire about details of the study and to consider their participation in the study. If, after reading the Subject Information Sheet and the ICF, consent is given to participate in the study, then the ICF must be signed and personally dated by the subject and the person conducting the informed consent discussion (and an impartial witness, if required). The subject will be provided with a copy of the signed ICF.

Verification of the signed ICF will be recorded in the subject's eCRF. The original signed ICF will be filed with the subject's records and/or in the Investigator Study File.

The Subject Information Sheet and ICF have to be approved by the IEC/IRB before they can be used in the study.

Confidential Page 87 of 175

The Subject Information Sheet and ICF must be revised whenever important new information becomes available that may be relevant to the subject's consent. Any revision of these documents must be approved by the IEC/IRB before they can be used in the study. Subjects must be informed in a timely manner if new information becomes available that may be relevant to their willingness to continue participation in the study. The communication of this information should be documented by having all parties concerned sign and personally date the revised ICF.

# Subject or Subject's Legally Acceptable Representative Unable to Read

If a subject is unable to read, or if a legally acceptable representative is unable to read, an impartial witness should be present during the entire informed consent discussion. After the ICF and any other written information provided to the subject, parent or guardian has been read and explained to the subject or the subject's legally acceptable representative, and after the subject or the subject's legally acceptable representative has orally consented to the subject's participation in the study and, if capable of doing so, has signed and personally dated the ICF, the witness should also sign and personally date the ICF. By signing the ICF, the witness attests that the information in the ICF and any other written information was accurately explained to, and apparently understood by, the subject or the subject's legally acceptable representative, and that informed consent was freely given by the subject or the subject's legally acceptable representative.

# Assent for Subjects Under the Age of Consent (Pediatric Subjects)

All subjects are under the age of consent (ie, pediatric subjects under 18 years of age); the written informed consent of a legally acceptable representative is required. Pediatric subjects who can understand the nature, scope, and possible consequences of the study must also give their assent, orally and/or in writing via the assent document, as appropriate. After the ICF and any other written information to be provided to subjects has been read and explained to the subject and the subject's legally acceptable representative, and after the subject and the legally acceptable representative have orally consented to the subject's participation in the study and, if capable of doing so, the subject has signed and personally dated the assent document, the legally acceptable representative should sign and personally date the ICF. By signing the ICF, the legally acceptable representative attests that the information in the ICF and any other written information was accurately explained to, and apparently understood by, the subject, and that assent was freely given by the subject.

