# 3.5 RATIONALE FOR STUDY DESIGN AND CHOICE OF TREATMENT GROUPS

It is recognized that performing clinical studies in young children or in subjects with reduced cognitive capacity presents particular practical and ethical issues. However, given the seriousness of DS, and the possible consequences of current inadequate treatments, the use of children with DS in this study is considered justified. Stratifying the randomization by age group is considered appropriate because the frequency and severity of major seizures can be higher in younger subjects. The two strata in the study will be subjects aged below 6 years and subjects aged 6-18 years. The study design has incorporated a titration period to enable subjects randomized to the high dose group adequate time to acclimate to this dose. Following the Titration Period, subjects will enter a 12-week Maintenance Period where they will continue on their randomized dose for the remainder of the study. The 12-week duration of the Maintenance Period is in keeping with the current standard study duration for evaluating the efficacy of chronic medications. Given the individual variability in seizure frequency and seizure type in this patient population, the primary endpoint, which seeks to compare an appropriate baseline of convulsive seizure frequency to the convulsive seizure frequency following treatment, is an appropriate primary endpoint for efficacy in this population.

Subjects will receive investigational medicinal product (IMP; ZX008 or placebo) in addition to their existing antiepileptic medications at their stable doses throughout the entire study. Thus, subjects receiving placebo will not be denied active therapy; they will continue to receive their existing medications at the exact same dosages. As the principal study measurement (convulsive seizures) might be considered subjective, a double-blind study design will prevent subjective bias. Upon study completion, eligible subjects will be able to receive ZX008 in an open-label extension study for up to 1 additional year of treatment.

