### 4.1 INCLUSION CRITERIA

Subjects meeting all of the following inclusion criteria may be enrolled into the study:

- 1. Subject is male or non-pregnant, non-lactating female, age 2 to 18 years, inclusive as of the day of the Screening Visit. Female subjects of childbearing potential must not be pregnant or breast-feeding. Female subjects of childbearing potential must have a negative urine pregnancy test. Subjects of childbearing or child-fathering potential must be willing to use medically acceptable forms of birth control (see Section 4.4), which includes abstinence, while being treated on this study and for 90 days after the last dose of study drug.
- 2. Subject must have documented medical history to support a clinical diagnosis of Dravet syndrome, where convulsive seizures are not completely controlled by current antiepileptic drugs.
- 3. Subjects must meet all of the following 5 criteria:
  - a. Onset of seizures in the first year of life in an otherwise healthy infant.
  - b. A history of seizures that are either generalized tonic-clonic or unilateral clonic or bilateral clonic, and are prolonged.
  - c. Initial development is normal.
  - d. History of normal brain MRI without cortical brain malformation.
  - e. Lack of alternative diagnosis.
- 4. Subjects must meet at least one of the following 3 criteria:
  - a. Emergence of another seizure type, including myoclonic, generalized tonic-clonic, tonic, atonic, absence and/or focal has developed after the first seizure type.

Confidential Page 36 of 175

- b. Prolonged exposure to warm temperatures induces seizures and/or seizures are associated with fevers due to illness or vaccines, hot baths, high levels of activity and sudden temperature changes and/or seizures are induced by strong natural and/or fluorescent lighting, as well as certain visual patterns.
- c. Genetic test results consistent with a diagnosis of Dravet syndrome (pathogenic, likely pathogenic, variant of unknown significance, or inconclusive but unlikely to support an alternative diagnosis.)
- 5. Subject must have had ≥4 convulsive seizures (tonic, tonic-atonic, tonic-elonic, clonic) per 4-week period for past 12 weeks prior to screening, by parent/guardian report to investigator or investigator medical notes.
- 6. All medications or interventions for epilepsy (including KD and VNS) must be stable for at least 4 weeks prior to screening and are expected to remain stable throughout the study.

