- 7. Subject has been informed of the nature of the study and informed consent has been obtained from the legally responsible parent/guardian.
- 8. Subject has provided assent in accordance with Institutional Review Board (IRB) requirements, if capable.
- 9. Subject's parent/caregiver is willing and able to be compliant with diary completion, visit schedule and study drug accountability.

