### 6.1.1 Screening, Clinic Visit 1 (Study Day -42)

Screening is the predetermined series of procedures with which each investigator selects an appropriate and representative sample of subjects for enrollment into the study. Select screening data will be documented in the IVR/IWR and eCRF.

Written informed parental or guardian consent and assent of minors (if the subject is capable of providing assent) must be obtained before a subject can start any of the screening procedures. The procedure(s) for obtaining written informed consent and assent of minor (if the subject is capable of providing assent) are described in Section 11.2.

The Screening visit will occur on Study Day -42; however, the procedures may be split over 2 consecutive days (e.g., Study Day -43 and Study Day -42 or Study Day -42 and Study Day -41). Splitting the visit procedures across 2 nonsequential days requires the approval of the medical monitor. The following procedures will be performed for all subjects before the start of seizure activity observation:

- Obtain written informed consent for the study
- Obtain written informed consent from parent/caregiver to collect PedsQL Family Impact, HADS, and EQ-5D-5L ratings of parent/caregiver symptoms and quality of life

Confidential Page 51 of 175

In cases where the screening period is extended beyond 42 days, the immediate 42 days before the Randomization visit will be used to calculate the baseline seizure frequency

- Review inclusion and exclusion criteria
- Record demographic information
- Record medical, neurological, and epilepsy history
- Record current epilepsy status (number/type/duration seizures per month)
- Collect past 6 months (or available duration) of parent/caregiver seizure diary data if available (screen shots of cell phones are acceptable, as are photocopies of paper diaries or print outs) and place in source file
- Record prior medications
- Complete physical examination, including height, weight, and calculation of BMI
- Complete neurological examination
- 12-lead electrocardiogram
- Doppler ECHO (this may be obtained any time between Study Day -42 and Study Day -21)
- Vital signs
- Urine pregnancy test for females of child-bearing potential
- Laboratory evaluation (serum chemistry, hematology, urinalysis, etc)
- Urine THC panel
- Whole blood CBD
- Obtain blood sample for epilepsy genotype panel
- C-SSRS Children's Baseline/Screening Assessment (Appendix 2)
- Instruct parent/caregiver on use of diary

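### Section 11.2 rests its consent rule on every subject being under 18, although 18-year-olds are eligible and others can turn 18 on study

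*Protocol*

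**What the plan says.** The protocol fixes the age range and the consent rule in separate places.

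**Age.** Inclusion criterion 1, in the synopsis and in Section 4.1, admits subjects "age 2 to 18 years, inclusive as of the day of the Screening Visit". Section 3.5 repeats the upper limit: "The two strata in the study will be subjects aged below 6 years and subjects aged 6-18 years". The study title and the primary objective (Section 2.1) refer to children and young adults.

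**Consent, specific provisions.** The subsection of Section 11.2 on assent opens with "All subjects are under the age of consent (ie, pediatric subjects under 18 years of age" and continues that "the written informed consent of a legally acceptable representative is required". The subject's part is assent: "Pediatric subjects who can understand the nature, scope, and possible consequences of the study must also give their assent". Inclusion criterion 7 requires that "informed consent has been obtained from the legally responsible parent/guardian", and criterion 8 adds assent if the subject is capable. The Screening procedure in Section 6.1.1 reads: "Written informed parental or guardian consent and assent of minors (if the subject is capable of providing assent) must be obtained".

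**Consent, general provision.** The main text of Section 11.2 makes the investigator responsible for the subject's written consent and says "the ICF must be signed and personally dated by the subject and the person conducting the informed consent discussion".

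**Renewed consent.** Section 11.2 calls for a revised form to be signed when important new information appears. Section 8.9.1 calls for a new consent, signed by the parent or guardian with the child's assent, if treatment is to continue after certain echocardiogram findings. Neither is triggered by a subject's age.

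**The concern.** The protocol itself places the age of consent at 18 and then says that nobody in the study has reached it. Criterion 1 makes that statement false for anyone aged 18 at Screening. The false statement matters because the rule that follows is built on it: a representative consents, and the subject at most assents. A site enrolling an 18-year-old finds three provisions (the assent subsection, criterion 7 and the Screening procedure) that treat the subject as a minor, and one (the main text of Section 11.2) that asks for the subject's own signature. Nothing says which prevails.

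The same gap opens later for a subject who enters at 17 and turns 18 while still being treated or followed up.

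What is at stake is participant protection. Section 1.2 records that fenfluramine products were withdrawn from the USA market after reports of heart valve disease and pulmonary hypertension. Whether a capable adult personally agrees to take the drug should not depend on which paragraph the site happens to read.

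**Working it through.** The protocol states no figure to reproduce. The check compares the provisions and adds some date arithmetic.

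**Step 1. Age limits**

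| Place | Ages covered |
|---|---|
| Synopsis and Section 4.1, criterion 1 | 2 to 18, inclusive, at Screening |
| Section 3.5, upper stratum | 6 to 18 |
| Section 11.2, assent subsection | all under 18 |

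A subject aged 18 at Screening satisfies the first two rows and falls outside the third. All three are current text, not part of the amendment summaries.

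**Step 2. Whose agreement each provision asks for**

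| Place | Consent | Subject's own role |
|---|---|---|
| Section 11.2, assent subsection | legally acceptable representative | assent, if able to understand |
| Section 4.1, criteria 7 and 8 | parent or guardian | assent, if capable |
| Section 6.1.1 | parent or guardian | assent of minors, if capable |
| Section 11.2, main text | subject | signs and dates the form |

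Only the last row provides for a capable 18-year-old's own consent. The first three can be met without it. The Section 6.1.1 wording covers assent of minors, so it describes no role at all for a subject who is no longer a minor.

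**Step 3. Turning 18 on study**

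The study calendar runs from Day -1 to Day 1 with no Day 0.

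- Screening (Day -42) to Visit 13 (Day 113): 42 + 113 - 1 = 154 days = 22 weeks, which agrees with the 6 + 14 + 2 weeks in Section 3.3. This is about 5 months, so a subject aged about 17 years 7 months or more at Screening turns 18 by Visit 13.
- Screening to the latest scheduled cardiac follow-up (Day 281): 42 + 281 - 1 = 322 days, or between 10 and 11 months. A subject aged about 17 years 1 to 2 months or more at Screening turns 18 by then. This longer period applies to subjects who stop early or do not enter the extension study (Section 6.4).

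**Step 4. Is reaching 18 dealt with anywhere?**

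The two triggers for a further signature are important new information (Section 11.2) and echocardiogram findings (Section 8.9.1). Neither depends on age, and the second again names the parent or guardian.

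**Step 5. Can the number affected be derived?**

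No. The protocol guarantees at least 40% of subjects in each age group but gives no distribution of ages within 6 to 18 years and no proportion with capacity to consent.

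**The case against.** There is a fair case that the practical gap is narrow.

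- **A route to the subject's own signature exists.** The main text of Section 11.2 has the subject sign and date the form and requires consent documents to follow GCP and local law. The subsection on persons unable to read speaks of the subject or the representative. Section 11.1 requires compliance with national requirements. This stands, and it is why the text supports saying only that a capable 18-year-old could be enrolled without their own consent. It does not remove the conflict, because the eligibility criterion and the Screening procedure can be met on a parent's signature.
- **Many adults with Dravet syndrome may lack capacity.** Section 1.1 describes cognitive impairment and says that the vast majority of those surviving to adulthood are wholly dependent on caregivers. For them a representative's consent may well be the right route. This stands as to size. But the assent subsection rests its rule on age, not capacity, and the protocol elsewhere expects some subjects to be capable.
- **Assent is required.** True, from subjects able to understand. It would therefore be wrong to say that a representative's consent is all the protocol asks. Assent is still a different act from consent.

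A reader might go further and infer that data from affected subjects would be lost and power reduced. The documents do not support this. The mITT Population used for the primary analysis (Section 10.2.2) is defined by randomization, one dose and one week of diary data. The Per Protocol Population (Section 10.2.3) requires completion of Maintenance and excludes only major deviations with a significant impact on clinical outcome. Section 4.5 keeps data collected up to discontinuation. None of these removes a subject for a consent defect.

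A reader might also estimate a headcount by spreading ages evenly over 6 to 18. No such distribution is given, and a count of 18-year-olds would not in any case be a count of capable subjects lacking their own consent.

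**Conclusion.** The sentence in Section 11.2 is wrong as written. It is contradicted by inclusion criterion 1, and the consent rule built on it does not fit every eligible subject. If the assent subsection, criterion 7 and Section 6.1.1 are followed literally, a capable 18-year-old could be enrolled without giving their own consent, and a subject who turns 18 on study would not be asked to consent on that ground.

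This is an internal inconsistency of low severity. The number affected cannot be derived from the protocol and is probably small. No sample-size, power or type I error figure is affected. The conclusion needs no outside law on the age of majority, because the threshold of 18 is the protocol's own. It assumes only that the provisions are read as they stand.

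**What to change.** In Section 11.2, replace the sentence stating that all subjects are under the age of consent with two cases:

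- **Under 18:** written consent of the legally acceptable representative, plus the subject's assent if capable.
- **Aged 18 at Screening, or reaching 18 on study:** the subject's own written consent, or re-consent on reaching 18, if capable; otherwise a legally acceptable representative's consent under applicable national requirements.

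Then bring the other provisions into line: inclusion criterion 7 (synopsis and Section 4.1), the consent step in Section 6.1.1, and the main text of Section 11.2 on who signs. The new-consent steps in Section 8.9.1 should refer to the same two cases. Criterion 1 can stay as it is if the consent text is changed to match it.

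The cost is wording in the protocol and consent forms, with the usual ethics committee approval, and an additional signature for what are probably few subjects. No design, endpoint or analysis element changes.
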